## 3 Considerations for data analyses and Data Handling Conventions

## 3.1 Baseline Definition

For all endpoints, the Baseline value will be the Day 1 (Visit 2) pre-brushing assessment with a non-missing value.

Unless otherwise stated, if Baseline data is missing no derivation will be performed and the Baseline value will be set to missing.

## 3.2 Subgroups/Stratifications

Subjects who satisfy all selection criteria will be randomized into the study. Randomization numbers will be assigned in ascending numerical order as each subject is determined to be fully eligible.

Subjects will be stratified by the maximum Baseline Schiff sensitivity score of their two selected test teeth. The stratification factor will give rise to two strata.

- **Stratum 1:** Maximum Schiff sensitivity score = 2
- **Stratum 2:** Maximum Schiff sensitivity score = 3

Within each stratum, subjects will be randomized to test toothpaste, negative control, or positive control with 2:2:1 allocation ratio using permuted randomized blocks.

## 3.3 Centers Pools

Since this is single center study, pooling of centers is not applicable.

## 3.4 Timepoints and Visit Windows

The timepoints and visits for this study are defined in the Table 1-1 "Schedule of Activities". Any deviation from the study schedule may be reviewed on case-by-case basis at the Blind Data Review Meeting (BDRM) to determine whether the data should be excluded from the Per-Protocol (PP) population.

## 4 Data Analysis

Data analysis will be performed by **CC** with oversight from GlaxoSmithKline Consumer Healthcare (GSK CH). The statistical analysis software used will be SAS version 9.4 or higher.

Prior to database closure a BDRM will be conducted in which various aspects of the trial will be discussed and agreed.

GlaxoSmithKline Consumer Healthcare Confidential Statistical Analysis Plan Template v6.0 Page 13 of 36

One aspect that will be considered prior to or during the BDRM is the assessment of the number of subjects who have dropped or discontinued from the study due to pandemic related events (e.g., Coronavirus Disease of 2019 [COVID-19]) and the potential need of a sensitivity analysis. Any major changes to planned analyses will need an amendment to SAP.

Except as described below, all listings will be produced for all randomized subjects.

## 4.1 **Populations for Analysis**

Tables described in this section will be produced for all randomized subjects.

## 4.1.1 Subject Disposition

Screen failures are defined as subjects who consent to participate in the clinical study but are not subsequently randomized. An enrolled subject is a subject who has signed informed consent and is eligible to proceed beyond the screening visit.

The number of subjects screened, enrolled, and randomized will be presented in Table 14.1.1.

The number and percentage of screen failure subjects (subjects not randomized) with reasons why subjects are not randomized including percentage of subjects not randomized due to COVID-19 pandemic will be displayed. Percentages for screen failure subjects will be based on the total number of subjects screened.

The number and percentage of randomized subjects who complete and discontinue the study, broken down by reason for discontinuation including percentage of subjects discontinued/withdrew from study due to COVID-19 pandemic, by study product and overall will also be displayed. The percentages will be based on the number of subjects randomized.

Table 14.1.1 will also present the number and percentage of subjects in each of the defined analysis populations (as defined in Section 4.1.3) by study product and overall. Percentages will be based on the number of subjects randomized.

Subject disposition including demographic data (age, sex, and race), screening date, study product start date and time, subject status (completer, Yes/No), study completion /withdrawal date, duration (in days) in the study (defined as [(date of completion or withdrawal – start date of study product) + 1], and the primary reason for withdrawal will be listed (Listing 16.2.1.1) by study product.

Subject disposition information will be listed for non-randomized subjects (Listing 16.2.1.2), displaying subject number, demographic information (age, sex, and race), screening date, reason for screen failure and any further details of reason for screen failure and discontinuation status due to COVID-19 pandemic.

## 4.1.2 Protocol Deviations

Protocol deviations will be tracked by the study team throughout the conduct of the study. Data will be reviewed prior to unblinding and closure of the database to ensure all important

GlaxoSmithKline Consumer Healthcare Confidential

Statistical Analysis Plan Template v6.0

Page 14 of 36

deviations are captured and categorized. Subjects with important protocol deviations liable to influence the efficacy outcomes will have affected data excluded from the PP population. Subjects may also be identified as having important protocol deviations not leading to exclusion of data from the PP population.

Important deviations of the protocol procedures may include, but will not necessarily be limited to the following:

- Consent procedures
- Inclusion/Exclusion criteria
- Concomitant medication/therapy
- Study procedures
- Randomization procedures
- Study drug dosing/study product administration/study product compliance
- Visit schedule/interval
- Other

The specific details of the important protocol deviations will be listed in Protocol Deviation Management Plan and the assessment process will be specified in the Blind Data Review Plan. Subjects with important protocol deviations will be identified at the BDRM.

The number and percentage of subjects with at least one important protocol deviation, with at least one important protocol deviation not leading to exclusion from PP population (overall and by each deviation reason) and at least one important protocol deviation leading to exclusion from the PP population (overall and by each deviation reason) will be presented by study product (Table 14.1.2) and listed in Listing 16.2.2.1.

All protocol deviations collected on the protocol deviation case report form page will be listed in Listing 16.2.2.2. The listing will present date of deviation, type of deviation, and deviation description.

## 4.1.3 Analysis Populations

Three analysis populations are defined.

Population	Definition / Criteria	Analyses Evaluated
Safety	Comprise of all randomized subjects who complete at least one use of study product. Any subject who receives a randomization number will be considered to have been randomized. This population will be based on the treatment the subject actually received*.	Demographics Safety

GlaxoSmithKline Consumer Healthcare Confidential Statistical Analysis Plan Template v6.0

Page 15 of 36

Population	Definition / Criteria	Analyses Evaluated
Modified Intent- To-Treat (mITT)	Comprise all randomized subjects who complete at least one use of study product and have at least one post-Baseline efficacy assessment. Any subject who receives a randomization number will be considered to have been randomized. This population will be based on the study product to which the subject was randomized.	Demographics Compliance Efficacy Analysis
	Comprise all subjects in the mITT population who have at least one assessment of efficacy considered unaffected by protocol violations.	
Per-Protocol	Protocol deviations that may exclude subjects from the PP population are defined in Section 4.1.2 (Protocol Deviations).	Demographics Efficacy Analysis
	This population will be based on the study product to which the subject was randomized.	

#### NOTES:

\* The treatment actually received will be assumed to be the same as the randomized treatment unless a protocol deviation is recorded to indicate that incorrect treatment was dispensed to the subject.

Please refer to Appendix 1: List of Data Displays which details the population to be used for each display being generated.

The numbers of subjects included in each of the analysis populations, will be summarized (Table 14.1.1). Subjects excluded from any of the analysis populations will be listed in Listing 16.2.3.1, with the reason for exclusion.

The primary population for assessment of efficacy will be the mITT Population. A PP analysis will be performed on the primary endpoint only if more than 10% of mITT subjects are excluded from the PP Population. A decision on whether a PP analysis will be performed will be made prior to study unblinding (release of the randomization codes).

## 4.2 Subject Demographics and Other Baseline Characteristics

#### 4.2.1 Demographic Characteristics

Descriptive statistics (number of subjects [n], mean, standard deviation [SD], median, minimum, and maximum for continuous variables and frequency count [n] and percentage [%] of subjects for categorical variables) will be presented for demographic variables by study product. These variables include age, sex, race, and stratification group and will be presented for the Safety population (Table 14.1.3.1), the mITT population (Table 14.1.3.2) and the PP population (Table 14.1.3.3).

Demographic information will be listed (Listing 16.2.4.1) for all randomized subjects.

GlaxoSmithKline Consumer Healthcare Confidential CCI Statistical Analysis Plan Template v6.0 Page 16 of 36

#### 4.2.2 General Medical History

Medical and surgical history (in the last year) including allergies or drug sensitivity will be listed in Listing 16.2.4.2, with start date and end date or ongoing at the start of study product.

# 4.3 Treatments (Study Product, Rescue Medication, other Concomitant Therapies, Compliance)

Randomization details will be listed, including the randomization number, stratification group, the planned study product, the actual study product the subject was randomized to and the randomization date (Listing 16.1.7.1) for all randomized subjects.

#### 4.3.1 Study Product Compliance and Exposure

Compliance data will be summarized for the mITT population and will be assessed by number of brushings.

Number of expected brushings, number of actual brushings, brushing compliance (%), number of missed brushings and number of additional brushings will be summarized using descriptive statistics by cumulative visit and by study product in Table 14.2.1.1.

Number of expected brushings at visit  $X = 2 \times$  Number of days between Visit 2 and Visit X.

Number of actual brushings = (Number of expected brushings) – (Number of missed brushings) + (Number of additional brushings).

% Compliance at 'Visit X' = (Number of actual brushings prior to Visit X / Number of expected brushings prior to Visit X)  $\times$  100.

Study product compliance (number of expected brushings, number of actual brushings, brushing compliance [%], number of missed brushings and number of additional brushings) will be listed in Listing 16.2.5.1 for all randomized subjects by study product.

Supervised study product brushings will also be summarized for the mITT population in Table 14.2.1.2 by visit. Supervised acclimatization product brushings at the Screening visit will be summarized for the mITT population in Table 14.2.1.3. Supervised study product application (subject number, date of visit and time of the supervised procedure) will be listed (Listing 16.2.5.2) for all randomized subjects. Supervised acclimatization product application (subject number, date of visit and time of supervised procedure) will be listed (Listing 16.2.5.3) for all randomized subjects.

## 4.3.2 Prior and Concomitant Medication

Prior medications/treatments, including prescription and non-prescription drugs, dietary supplements and herbal remedies, taken in the last 30 days and prior to signing the informed consent form, will be documented in the CRF. The prior and concomitant medications will be coded using a validated medication dictionary, World Health Organization Drug Dictionary (WHODD).

GlaxoSmithKline Consumer Healthcare Confidential CCI Statistical Analysis Plan Template v6.0 Page 17 of 36

Prior medications and prior non-drug treatments will be listed by subject, with drug name, WHODD Drug Synonym, reason, route, dose, frequency, start date and end date both relative to study product start date (Listing 16.2.4.3) for all safety population Prior medications are defined as those which stopped before the first use of the study product.

Concomitant medications and concomitant non-drug treatments/significant non-drug therapies taken during treatment will be listed similarly (Listing 16.2.4.4) for all safety population with either ongoing or end date displayed. Concomitant medications are defined as medications that started or stopped on or after the first use of the study product or are ongoing.

Unknown dates will not be imputed, however if the start or stop date is unknown, then it will be assumed to be concomitant medication unless the partial start date or stop date indicates differently.

## 4.4 Analysis of Efficacy

The primary population for assessment of efficacy will be the mITT Population.

## 4.4.1 Primary Efficacy Endpoint

#### 4.4.1.1 Primary Efficacy Endpoint Definition

The primary efficacy variable is the change from Baseline in Schiff sensitivity score at 12 weeks, derived as the average score of the 2 test teeth (identified at Baseline). The change from Baseline is derived from the individual teeth first before calculating the average change of the 2 test teeth.

Descriptive statistics (n, missing, mean, SD, standard error [SE], median, minimum, and maximum) will be presented for Schiff sensitivity score calculated as the average score of the 2 test teeth at each assessment time point together with the change from Baseline in Table 14.2.2.1.1 for all subjects in the mITT population by study product. Raw means ( $\pm$  SE) of the Schiff sensitivity score at each time point will be plotted by study product in Figure 14.2.2.1.4 for all subjects in the mITT population.

Individual data for Schiff sensitivity score will be listed for each subject by study product group and visit in Listing 16.2.6.1 for all randomized subjects.

## 4.4.1.2 Statistical Hypothesis, Model, and Method of Analysis

The primary comparison is between the test toothpaste and the negative control in the mITT population. As there is only a single primary objective no adjustment for multiple comparisons is required.

Study product differences will be tested under the null hypothesis at Week 12:

- H0: there is no difference between test product and negative control;
- H1: there is a difference between test product and negative control;

GlaxoSmithKline Consumer Healthcare Confidential Statistical Analysis Plan Template v6.0 Page 18 of 36

Change from Baseline in Schiff sensitivity score will be analyzed using a Mixed Model with Repeated Measures (MMRM), with study product, visit and study product by visit interaction as fixed effects, and Baseline Schiff sensitivity score as a covariate. Subject will be included as a repeated measure with unstructured covariance matrix. Kenward Rogers degrees of freedom approach will be applied (Kenward and Roger, 1997). If the model with unstructured covariance matrix does not converge then compound symmetry covariance matrix will be used.

Using the above model, adjusted mean change from Baseline, along with 95% confidence intervals (CIs) will be reported by study product. P-values testing for non-zero change from Baseline will be presented for all study products. Mean difference between study products at Week 12 (test toothpaste compared to negative control), 95% CIs and p-values will be provided for Schiff sensitivity score in Table 14.2.2.1.2. Significance testing will be conducted at the two-sided 5% significance level.

The assumption of normality and homogeneity of variance in the MMRM will be investigated. In case of violation of these assumptions, a suitable non-parametric test (the Van Elteren test, adjusted for the randomization stratification) will be performed to assess change from Baseline comparisons (test toothpaste vs. negative control at Week 12) and the results will be provided to support the MMRM results. The non-parametric results will be considered confirmatory under the observation of strong violations of the assumptions.

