## 12.3.1 Primary Analysis

The primary endpoint of this study is the change from Baseline in the Schiff sensitivity score at Week 12; the primary hypothesis test will be the comparison between the test toothpaste and the negative control in the mITT population.

Change from Baseline in Schiff sensitivity score will be analysed using a Mixed Model with Repeated Measures (MMRM), with study product, visit and study product by visit interaction as fixed effects, and Baseline Schiff sensitivity score as a covariate. Subject will be included as a repeated measure with unstructured covariance matrix. Kenward Rogers degrees of freedom approach will be applied (Kenward and Roger, 1997). The difference between least square means for the test toothpaste compared to the negative control at Week 12 will be presented along with two-sided p-value and 95% CIs.

As a sensitivity analysis, the change from Baseline in Schiff sensitivity score at Week 12 will be compared between study products (test toothpaste vs. negative control) using an Analysis of Covariance (ANCOVA) model with study product as a fixed effect and Baseline Schiff sensitivity score as a covariate.

The assumption of normality and homogeneity of variance in each MMRM will be investigated. In case of violation of these assumptions, a suitable non-parametric test (adjusted for the randomisation stratification) will be performed to assess change from Baseline comparisons (test toothpaste vs. negative control at Week 12) and the results will be provided to support the MMRM results; the non-parametric results will be considered confirmatory under the observation of strong violations of the assumptions.

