Subjects will also be shown a list of the ingredients contained in the test products to confirm they have no known allergies or hypersensitivity to any of the ingredients.

2. Send study information video (at Screening) and brushing instruction video (at Baseline) to subjects using WeChat.

3. Qualifying tactile threshold (g) and Schiff sensitivity scores can be recorded on paper source documents for later transcription into the electronic case report form (eCRF).

4. Prior to clinical examinations and assessments, subjects will be shown or reminded how to complete a VAS. Evaporative (air) assessments follow the tactile assessments, with minimum 5 minutes between last tactile assessment and first evaporative (air) assessment (to allow tooth recovery).

- Visits 1 and 2: maximum force for tactile assessments = 20g
- Visits 3 and 4: maximum force for tactile assessments = 80g

The clinical examiner should communicate their Schiff sensitivity score to the scribe (non-verbally) before the subject completes the VAS. Examiner and subject should be blinded to each other's scores. VAS is a qualifying assessment at Baseline ONLY.

5. Test teeth must only be selected from eligible teeth (no dentition exclusions, presence of EAR, MGI = 0 adjacent to the test area only, clinical mobility = 0) with a tactile threshold ≤ 20 g and a Schiff sensitivity score ≥ 2 at both Screening and Baseline, and VAS ≥ 40 mm at Baseline.

Test teeth must have the same Schiff sensitivity score at Screening and Baseline (i.e., Schiff sensitivity score = 2 at Screening and Baseline, or Schiff sensitivity score = 3 at Screening and Baseline)

6. Return study supplies to subject after supervised brushing.

7. Subjects randomized to test toothpaste only: Dispensing staff will show the subject the location of their two test teeth prior to supervised brushing.

8. Record AEs from signing of the informed consent form (ICF) until 5 days after last use of study product (or the last study procedure).

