## 4.4.2.2.1 Statistical Hypothesis, Model and Method of Analysis

Two comparisons will be considered for this secondary endpoint. Firstly, the comparison between the test toothpaste and the negative control in the mITT population. Secondly, the comparison between the positive control and the negative control in the mITT population.

- 1. Study product differences will be tested under the null hypothesis at Week 6 and Week 12:
- H0: there is no difference between test product and negative control;
- H1: there is a difference between test product and negative control;
- 2. Study product differences will be tested under the null hypothesis at Week 6 and Week 12:
- H0: there is no difference between positive control and negative control;
- H1: there is a difference between positive control and negative control;

GlaxoSmithKline Consumer Healthcare Confidential Statistical Analysis Plan Template v6.0 Page **21** of **36** 

Change from Baseline in tactile threshold (g) will be analyzed using the same MMRM as the primary endpoint but with Baseline tactile threshold (g) as a covariate, rather than Baseline Schiff sensitivity score. In addition, the maximum Baseline Schiff sensitivity score of the two test teeth (2 or 3) will be fitted as a fixed effect.

Using the above model, adjusted mean change from Baseline, along with 95% CIs will be reported by study product. P-values testing for non-zero change from Baseline will be presented for both study products. Mean difference between study products, 95% CIs and p-values will be provided for Tactile Threshold (g) score in Table 14.2.3.1.2. Significance testing will be conducted at the two-sided 5% significance level.

The assumption of normality and homogeneity of variance in the MMRM will be investigated. In case of violation of these assumptions, a suitable non-parametric test (the Van Elteren test, adjusted for the randomization stratification) will be performed to assess change from Baseline comparisons (test toothpaste vs. negative control and positive control vs. negative control at Weeks 6 and 12) and the results will be provided to support the MMRM results; the non-parametric results will be considered to supersede the MMRM results under the observation of strong violations of the assumptions.

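### The primary Schiff MMRM shares one Baseline slope across Weeks 6 and 12, which can leave the Week 12 standard error slightly too large

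*SAP*

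**What the plan says.** The primary endpoint is the change from Baseline in Schiff score at Week 12, "derived as the average score of the 2 test teeth (identified at Baseline"). Both documents analyse it with an MMRM. The SAP (4.4.1.2) fits the model "with study product, visit and study product by visit interaction as fixed effects, and Baseline Schiff sensitivity score as a covariate"; Protocol 12.3.1 has "study product by visit interaction as fixed effects, and Baseline Schiff sensitivity score as a covariate". On the residual side, "Subject will be included as a repeated measure with unstructured covariance matrix". Baseline enters as a main effect only.

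The supporting analysis (SAP 4.4.1.3) is a Week 12 ANCOVA on product and Baseline Schiff, so its slope is estimated from Week 12 alone. SAP 4.4.3 and Protocol 12.3.6 present the difference between the two methods as one of missing-data assumptions: missing at random for the MMRM, missing completely at random for the ANCOVA.

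On stratification, SAP 3.2 says "Subjects will be stratified by the maximum Baseline Schiff sensitivity score of their two selected test teeth", "with 2:2:1 allocation ratio using permuted randomized blocks". The tactile model adds that stratum (SAP 4.4.2.2.1: "In addition, the maximum Baseline Schiff sensitivity score of the two test teeth (2 or 3) will be fitted as a fixed effect"), the VAS model inherits it, and the Van Elteren fallback is stratified. The Schiff MMRM and ANCOVA have no separate stratum term.

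**The concern.** Schiff is bounded at 0. A subject whose two teeth average 3 can fall by 3 points; one averaging 2 can fall by only 2. As the effect builds from Week 6 to Week 12, the relation between Baseline and change may steepen. A shared slope would then be a compromise that fits neither visit well, and the misfit goes into the Week 12 residual variance and so into the standard error of the contrast that decides study success.

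There is also a matter of interpretation. If the MMRM and ANCOVA disagree at Week 12, a reader of SAP 4.4.3 will put it down to missing data. With a shared slope in one model and a Week 12 slope in the other, they can disagree with complete data.

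**Working it through.** **1. The plan's own figure.** Two-sample t-test, 94 per arm, difference 0.3, SD 0.6 (SAP 1.4): noncentrality 0.5 × √(94/2) = 3.43 on 186 degrees of freedom, two-sided 5%. Power is 92.65%, as stated. No covariate enters, so nothing below changes it.

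**2. What the shared slope does.** Let D be the test-minus-control difference in mean Week 12 change and B the difference in mean Baseline Schiff. Product by visit is fully fitted, so with complete data:
- MMRM as planned: contrast = D − b(shared) × B
- Week 12 ANCOVA: contrast = D − b(Week 12) × B
- MMRM with Baseline by visit: the same as the ANCOVA

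Randomisation makes B zero on average, so all three are unbiased.

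**3. Effect on the model standard error.** Assumed, because the documents do not give them: 50%, 20% and 30% of subjects with mean Baseline 2, 2.5 and 3, and similar residual variances at the two visits, so that the shared slope lies about midway. The mean is 2.4 and the Baseline variance is 0.5 × 0.4² + 0.2 × 0.1² + 0.3 × 0.6² = 0.19. If the slopes differ by d, the Week 12 slope is wrong by d/2 and the residual variance carries an excess of (d/2)² × 0.19. Taking 0.6² = 0.36 as the variance that includes this excess:
- d = 0: no excess, no change
- d = 0.3: excess 0.0225 × 0.19 = 0.0043; √(0.3557/0.36) = 0.994, so the SE falls 0.6% when the term is added
- d = 0.6: excess 0.09 × 0.19 = 0.0171; √(0.3429/0.36) = 0.976, so the SE falls 2.4%

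Simulation agrees (1,500 trials per row, 235 subjects, stratified 2:2:1 blocks, same score mix, Week 6-12 correlation 0.6):

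| Slopes, Week 6 / Week 12 | Mean SE, shared slope | Mean SE, Baseline by visit | Reduction |
|---|---|---|---|
| −0.3 / −0.3 | 0.0880 | 0.0880 | nil |
| −0.2 / −0.5 | 0.0884 | 0.0879 | 0.6% |
| −0.1 / −0.7 | 0.0904 | 0.0882 | 2.4% |

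A second set of assumptions (residual variances 0.30 and 0.33, correlation 0.57) gave variance reductions of 1.6% for slopes −0.3/−0.6 and 8% for −0.2/−0.9. In SE terms these are 1 − √0.984 = 0.8% and 1 − √0.92 = 4.1%.

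**4. How much is real variability.** Little. The empirical SD of the estimate moved from 0.0903 to 0.0900 (slopes −0.2/−0.5) and from 0.0906 to 0.0899 (−0.1/−0.7). Stratification keeps B close to zero, so the wrong slope has little to multiply. With the same mix, Baseline varies freely only within stratum 2: variance 0.5² × 0.4 × 0.6 = 0.06, times that stratum's share of 0.5, is 0.03. The SD of B is about √(0.03 × 2/94) = 0.025. The gap between MMRM and ANCOVA with no data missing is then typically (d/2) × 0.025, which is 0.004 Schiff points for d = 0.3 and 0.008 for d = 0.6, against an assumed effect of 0.3.

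**5. The stratum.** Each test tooth is fixed at "Schiff sensitivity score = 2 at Screening and Baseline, or Schiff sensitivity score = 3 at Screening and Baseline". The mean of two such teeth is 2, 2.5 or 3. A mean of 2 is stratum 1; 2.5 or 3 is stratum 2. The covariate therefore determines the stratum, and a stratum term can add only curvature across three points. For the mix above, the stratum indicator has variance 0.25 and covariance with Baseline (0.2 × 2.5 + 0.3 × 3) − 2.4 × 0.5 = 0.20, so the linear term explains 0.20²/(0.19 × 0.25) = 84% of it and leaves 0.0395. An assumed stratum step of 0.3 points would remove 0.09 × 0.0395 = 0.0036 from 0.36. The SD becomes 0.597 and the power 92.88%. Over the other mixes tried, the most reached was 92.99%. With a linear relation the gain is zero.

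**The case against.** A reader might infer a stronger point: that the primary model drops the randomisation stratum which the tactile, VAS and Van Elteren analyses keep, and so gives up precision. The documents do not support that. Baseline tactile threshold and Baseline VAS do not determine the Schiff stratum, and Van Elteren has no covariate, so those analyses need it explicitly. Baseline Schiff does determine it. This is a coherent reason for the different models, although neither document states it. A stratum gain of about 5% of the variance can be produced, but only by placing subjects with one tooth at 2 and one at 3 a full 0.3 points off the line. That offset is as large as the whole assumed treatment effect and amounts to a stratum step of 0.6.

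The case against the slope point is also fair in part. The documents give no slopes, score mix or between-visit correlation, so a difference in slopes is plausible but not shown. The planned Week 12 ANCOVA already fits its own slope, and with about 2% dropout it uses nearly the same Week 12 data, so a material misfit would be visible there. The power statement never relied on covariate adjustment. All of this stands, and it limits the size of the point. It does not give a reason to keep the restriction, which costs one degree of freedom to lift and blurs the comparison that SAP 4.4.3 sets up.

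**Conclusion.** The point holds as a minor improvement. The shared slope leaves the Week 12 contrast unbiased. Its model standard error is unchanged with equal slopes, about 0.6-0.8% too large if they differ by 0.3, and about 2.4-4% too large if they differ by 0.6-0.7. The gain from the extra term is a slightly tighter, better-calibrated interval; the true sampling variability hardly moves. The size depends on assumed slopes, score mix and correlation. The simulations used model-based generalised least squares standard errors, not full Kenward-Roger.

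It would go too far to say that the plan has lost precision by leaving out the stratum, that the slopes are known to differ, or that the 92.65% is in doubt.

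**What to change.** Before the randomisation codes are released, add Baseline Schiff by visit to the primary MMRM in SAP 4.4.1.2 and enter the change in SAP Table 5-1, since Protocol 12.3.1 has the model without it. With that term, the Week 12 MMRM and ANCOVA contrasts coincide when data are complete, and any gap reflects missing data as SAP 4.4.3 intends. If the codes are already out, report the extended model only as a labelled supplementary analysis.

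Optional, for consistency:
- Add the matching Baseline by visit term to the tactile and VAS MMRMs. No gain was computed for those endpoints.
- Either state that Baseline Schiff carries the stratum, or add maximum Baseline Schiff (2 or 3) to the Schiff MMRM and ANCOVA. This gains precision only if the Baseline relation is non-linear.

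Cost: one model degree of freedom, or two with the stratum, out of about 230, plus the model code and SAP wording. No new data are needed, and no simulated scenario showed a material loss. Changing the protocol text as well would need prospective GCP Office/IRB approval under Protocol 13.3.1; the Table 5-1 entry is the lighter route.
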